 - Examples of signs and symptoms include **but not limited to**: pain, burning, or tingling in a blister around the mouth or genitals, fingers, ears, **or any part of the body close to or far from the injection site**; eye pain, light sensitivity, discharge from the eyes, or blurry vision; weakness in arms or legs; extreme drowsiness; mental confusion.
 - If a patient answers "yes", then the following information about the infection will be collected: signs and symptoms, dates, reporting and testing for virus identification, and antiherpetic treatment received.
- Record the following information about IMLYGIC received: dates, dose concentration, injection volume.
- ¹ Record dates and types of other anticancer therapy received (see "f" for the list of therapies).
- ^k Record the following information about antiherpetic therapy received: dates, type (eg, acyclovir, valacyclovir, famciclovir, docosanol), administration route (oral, intravenous, topical).

Protocol Number: 20130193
Date: 12 October 2022
Page 7 of 62

Adverse events and serious adverse events that occur after the patient has signed the informed consent form (ICF) through 30 days after the last dose of IMLYGIC will be recorded in the electronic case report form (eCRF). Adverse events should be assessed on an ongoing basis.

- ^m Safety events which are considered serious must be submitted as individual case safety reports to Amgen via the applicable Amgen Safety Reporting Form (paper or electronic form) within 1 business day of Investigator's awareness.
- ⁿ Adverse events and serious adverse events that occur more than 30 days after the last dose of IMLYGIC and deemed by the Investigator to be related to treatment with IMLYGIC. **Any fatal outcome during long term follow up should be reported as a serious adverse event.**
- ^o Product complaints that occur after the patient has signed the ICF through 30 days after the last dose of IMLYGIC.
- P Other safety findings include, for example, medication errors, exposure to IMLYGIC during pregnancy and breastfeeding, accidental exposure, that occur after the patient has signed the ICF through 30 days after the last dose of IMLYGIC.
- ^q Record the following information on survival status: date of contact, status (eg, alive or deceased), and date and cause of death (if applicable).

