6.2 Rationale

Wild-type HSV-1, the parent virus of IMLYGIC, is commonly acquired during childhood, and seroprevalence in the United States is 54% among persons aged 14 to 49 years (Bradley et al, 2014) and 63% among pregnant women (Xu et al, 2007). HSV-1 is transmitted by direct contact with the mucocutaneous surfaces of an infected person. Most signs and symptoms present near the site of infection. The most common manifestation of HSV-1 infection is cold sores at the mucocutaneous junction. While typically the site of infection is oral or genital mucosa, the site can include other regions where there is contact exposure. Examples include herpetic whitlow on finger of dental professionals (Browning and McCarthy, 2012) and herpetic gladiatorum on the face and periorbital region of wrestling athletes (Anderson, 2003). While lesions are most likely to occur near the time of initial exposure, herpes viruses are known to establish latency in the regional neural root ganglia; and recurrences, typically in the same region, may occur over subsequent years (Engelberg et al, 2003). Fever, stress, and other factors

Protocol Number: 20130193 Date: 12 October 2022

are common triggers of recurrence. Frequent recurrences of cold sores are reported by 3% to 5% of the general population (Rooney et al, 1993).

HSV-1 infection may also include ocular HSV-1 infection, occurring at an incidence of 8 to 13 per 100,000 in the general population (Young et al, 2010). Ocular HSV-1 may present as herpetic conjunctivitis, keratitis, or uveitis. Life-threatening HSV-1 infections include herpetic encephalitis, occurring at an incidence of 1 to 3 per million (Hjalmarsson et al, 2007), and disseminated HSV-1 infection with fulminant multi-organ failure. Most case reports of disseminated HSV-1 infection are among immunocompromised persons, but may also occur in immunocompetent persons (Norvell et al, 2007; Watanabe et al, 2010). HSV-1 is generally not considered an opportunistic infection among immunocompromised persons. For example, human immunodeficiency virus (HIV) positive and HIV-negative men have a similar HSV-1 seroprevalence (Russell et al, 2001; Smit et al, 2007). However, immunocompromised persons with HSV-1 have more frequent recurrences and severe clinical manifestations than the general population with HSV-1 (Zuckerman et al, 2009).

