8.2.3.1 Inclusion Criteria

- Patient has provided written informed consent.
- Patient is an adult (≥ 18 years of age at the time of informed consent) with a diagnosis of melanoma.

Protocol Number: 20130193
Date: 12 October 2022
Page 21 of 62

 Patient enrolled within 1 month of receiving the first dose of IMLYGIC for the treatment of melanoma.

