8.2.5 Study Follow-up

The patient's follow-up begins at enrollment and continues through the earliest date of: 5 years after the first IMLYGIC dose, death, withdrawal of consent, or loss to follow-up. Study assessments are detailed in the Table 1. During IMLYGIC treatment, the study assessments for signs and symptoms of herpetic infection, safety, and survival are to be completed at the clinic visits for IMLYGIC treatment. After discontinuation of IMLYGIC until the end of follow-up, these study assessments are to be completed every 3 months (\pm 30 days) via phone or routine clinic visits if they fall within the 30-day window. Data collected will be transcribed into an electronic case report form (eCRF).

At any time that enrolled patients, their close contacts, or their HCPs develop a suspected herpetic lesion, they should seek medical attention to evaluate and swab any suspicious lesion for talimogene laherparepvec DNA testing (per the Postmarketing IMLYGIC Surveillance Program) or wild-type HSV-1 testing (per local standard of care) (Centers for Disease Control, 2010; Patel et al, 2010). The evaluation and reporting of suspected herpetic infections will be done according to the standard of care for IMLYGIC as described in the IMLYGIC USPI and the SmPC. In addition to these materials, for this study, patients will receive an information sheet about the study to share with their close contacts and HCPs. This information sheet will describe the study and will contain the study number for use in reporting a suspected herpetic infection.

For patients enrolled in this study, informed consent will be collected upon study enrollment to link test results from the existing Postmarketing IMLYGIC Surveillance Program to the patient (see Appendix E for a sample laboratory report from Viracor). The results will be captured in the eCRF and be included in the data analysis of the study. For close contacts and HCPs, test results from the Postmarketing IMLYGIC Surveillance Program will be linked to the study only and not to any identifiable patient information, such as the name or date of birth.

Subjects who have ended IMLYGIC treatment and entered into the follow-up period may be allowed to restart treatment if the investigator chooses. In such cases, after restarted IMLYGIC treatment is ended, subjects will continue in the follow-up period as outlined in the schedule of assessments.

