8.3.2.2 Secondary Endpoints

 Count of herpetic infections with detection of talimogene laherparepvec DNA among close contacts and HCPs

Herpetic infection includes oral or genital herpes, herpetic whitlow or herpetic gladiatorum of the skin, ocular herpes, herpetic encephalitis, and disseminated herpetic infection. For either swab samples or appropriate biological sample for disseminated infection, a specialty laboratory will use a qPCR test that is specific for talimogene laherparepvec DNA. Results will be reported as detectable talimogene laherparepvec DNA levels.

 Incidence rate of herpetic infection with detection of talimogene laherparepvec DNA among patients during treatment with IMLYGIC

The incidence rate will be summarized for detectable talimogene laherparepvec DNA results from the date of first IMLYGIC dose to the date of last IMLYGIC dose + 30 days. If patients receive IMLYGIC over multiple treatment phases, the treatment period is defined as the sum of time from the date of first IMLYGIC dose to 30 days after the date

Protocol Number: 20130193 Date: 12 October 2022

of last IMLYGIC dose or the day before the subsequent treatment phase, whichever comes first, in each treatment phase.

 Incidence rate of herpetic infection with detection of talimogene laherparepvec DNA among patients after discontinuation of IMLYGIC

The incidence rate will be summarized for detectable talimogene laherparepvec DNA results during the period from 31 days after the last dose of IMLYGIC through the end of follow-up. If patients receive IMLYGIC over multiple treatment phases, each post-treatment period is defined as sum of time from 31 days after date of last IMLYGIC dose in the prior treatment phase to 1 day prior to the date the first IMLYGIC dose in the subsequent treatment phase or the end of study.

 Incidence rate of herpetic infection with detection of wild-type HSV-1 among patients during treatment with IMLYGIC

For either swab samples or appropriate biological sample for suspected herpetic infection, tests that are specific for wild-type HSV-1 should be performed per local standard of care (Centers for Disease Control, 2010; Patel et al, 2010). Results will be reported as either positive or negative for HSV-1.

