8.7.2.4 Analysis of the Primary and Secondary Endpoints

8.7.2.4.1 Analysis of the Primary Endpoint

Incidence of herpetic infection with detection of talimogene laherparepvec DNA
among patients. Herpetic infection includes oral herpes, genital herpes, herpetic
whitlow or herpetic gladiatorum of the skin, ocular herpes, herpetic encephalitis, and
disseminated herpetic infection.

The incidence rate will be calculated as the number of suspected herpetic infections that are detectable for talimogene laherparepvec DNA divided by sum of follow-up time (last date of follow-up minus the date of first IMLYGIC dose) in patient-years. As a measure of precision, a 95% confidence interval will be calculated around the incidence rate.

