Patient incidence (n and %) of adverse events and serious adverse events occurring after the date of last IMLYGIC dose plus 31 days will be reported. If patients receive IMLYGIC over multiple treatment phases, the adverse events and serious adverse events collection period is defined as 31 days after date of last IMLYGIC dose in the prior treatment phase to one day prior to the date of the first IMLYGIC dose in the subsequent treatment phase or the end of study.

Overall survival

Overall survival will be estimated using the Kaplan-Meier method with the time to death being calculated from the date of the first IMLYGIC dose.

Patients who are alive or lost to follow-up at the time of the analysis will be censored.

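### Rates, adverse-event incidence and survival are counted from the first dose although observation starts at enrolment, up to 1 month later, so early unobserved time can bias the rates slightly low

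*Protocol*

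**What the plan says.** **Start of observation.** Section 8.2.5: "The patient's follow-up begins at enrollment and continues through the earliest date of: 5 years after the first IMLYGIC dose", or death, withdrawal or loss if earlier. Entry is governed by section 8.2.3.1: "Patient enrolled within 1 month of receiving the first dose of IMLYGIC for the treatment of melanoma". The baseline visit (8.2.4) is a visit at which IMLYGIC is given, but not necessarily the first one.

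**Start of the primary clock.** Section 8.7.2.4.1 divides the number of DNA-positive suspected infections as follows: "divided by sum of follow-up time (last date of follow-up minus the date of first IMLYGIC dose) in patient-years". Section 8.3.2.1 restricts the results counted to those during follow-up.

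**Start of the on-treatment clock.** Section 8.3.2.2 sets the window for the talimogene laherparepvec rate "from the date of first IMLYGIC dose to the date of last IMLYGIC dose + 30 days". The wild-type HSV-1 rate and the on-treatment adverse-event incidence use the same window (8.3.2.2, 8.7.2.4.2).

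**Adverse-event collection.** The Table 1 footnotes limit recording to "Adverse events and serious adverse events that occur after the patient has signed the informed consent form (ICF) through 30 days after the last dose"; section 10.2 agrees.

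**Survival.** Section 8.7.2.4.2 specifies Kaplan-Meier with "time to death being calculated from the date of the first IMLYGIC dose". Delayed entry is not mentioned.

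**Baseline capture of infections.** Table 1 schedules the signs-and-symptoms question during and after treatment but not at baseline, where only the history of herpetic infection is taken. Patient qPCR results are marked as possible at any time.

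**The concern.** For a patient enrolled after the first dose, two statements in the protocol cannot both hold: follow-up begins at enrolment, and follow-up time is measured from the first dose. The second enters the formula, so the denominator contains days on which the patient was not yet under study observation.

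If infections on those days are not counted, the primary and on-treatment rates and their upper confidence limits come out too low. That is the unfavourable direction for a postmarketing safety requirement.

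Two neighbouring results have related problems:

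- **Adverse events.** The analysis window opens at the first dose, but collection opens at consent. Events in between are absent from the numerator of a reported n and %, while the patient stays in the denominator. Section 6.1 puts the second treatment visit at 3 weeks, so a patient enrolled at the end of the window may already have had two treatment visits.
- **Survival.** A patient who died between first dose and enrolment could not have joined. Counting that interval without delayed entry is left truncation, and it raises the curve.

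The limitations in section 8.9 do not mention the gap.

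**Working it through.** **Inputs from the protocol**
- 535 patient-years, about 300 patients, zero-event upper bound 6.9 per 1000, 80% detection probability at 3 per 1000, mean survival of about 2 years (8.5)
- Enrolment up to 1 month from first dose (8.2.3.1)
- Median treatment duration about 6 months in the trials (study design schema)

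**Assumptions.** The lag from dose to enrolment is not given. I take a mean of 15 days, and 30 days for every patient as the limit. I also assume constant hazard, no capture of infections before enrolment, and 535 as the total obtained with the protocol's own formula. The 6-month median stands in for the mean treatment time.

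**Step 1: reproduce the plan's figures**
- Zero-event upper bound, one-tailed 97.5%: −ln(0.025)/535 = 3.689/535 = 6.90 per 1000. This agrees.
- Detection probability at 3 per 1000: 1 − exp(−0.003 × 535) = 79.9%. This agrees with 80%.

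**Step 2: unobserved patient-years**
- 15 days: 300 × 15/365.25 = 12.3
- 30 days: 300 × 30/365.25 = 24.6

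**Step 3: primary rate**

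| | As written | 15-day lag | 30-day lag |
|---|---|---|---|
| Observed patient-years | 535 | 522.7 | 510.4 |
| Share unobserved | – | 12.3/535 = 2.3% | 24.6/535 = 4.6% |
| Zero-event upper bound per 1000 | 6.90 | 3.689/522.7 = 7.06 | 3.689/510.4 = 7.23 |
| Detection probability at 3 per 1000 | 79.9% | 79.2% | 78.4% |
| A true rate of 3.00 would be reported as | – | 3 × 522.7/535 = 2.93 | 3 × 510.4/535 = 2.86 |

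**Step 4: on-treatment rates.** The window is 6 months plus 30 days: 0.5 + 30/365.25 = 0.582 years per patient, or 174.6 patient-years for 300 patients.
- 15 days: 12.3/174.6 = 7.1%
- 30 days: 24.6/174.6 = 14.1%

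The share depends on time on treatment. With 3 months the window is 0.332 years, and the shares are 0.0411/0.332 = 12.4% and 0.0821/0.332 = 24.7%. With 12 months the window is 1.082 years, and they are 3.8% and 7.6%.

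**Step 5: survival.** The protocol gives no basis for an exact figure. As an illustration under constant mortality, conditioning on survival to enrolment lengthens mean survival by exactly the lag. That is 15 (30) days on about 730.5 days, or 2.1% (4.1%).

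**Step 6: what is not affected.** The post-discontinuation rates start 31 days after the last dose, so they are essentially untouched. Patients enrolled on or before the day of the first dose have no gap. Adverse-event incidence is n and %, so there the effect is missed events and not diluted person-time.

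**The case against.** The strongest reply has four parts.

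1. **Pre-enrolment infections may be captured.** A reader might infer that no event could be recorded before enrolment. The documents do not show that. Swab results come from a surveillance programme that exists independently of the study. Consent links those results to the patient with no stated date limit, and the baseline history asks about testing. Section 8.3.2.2 also words the on-treatment results as running from the first dose, so numerator and denominator nominally share a window there. This stands: capture is unclear, not zero. But section 8.3.2.1 ties the primary numerator to follow-up, which begins at enrolment, and nowhere does the protocol say that earlier positives are collected and counted.

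2. **Immortal time and early risk.** A reader might call the whole gap immortal time, or infer from "lesions are most likely to occur near the time of initial exposure" (6.2) that the highest-risk weeks are lost. Neither is supported. A patient can have an infection before enrolling and still enrol; only death is precluded. The quoted sentence belongs to a paragraph on wild-type HSV-1 and does not establish when IMLYGIC infection would peak.

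3. **The lag is assumed and the effect is small against sampling error.** This stands. At 3 per 1000, 535 patient-years yield about 1.6 events. The exact 95% interval is about 0.05 to 10.4 per 1000 for one event and 0.45 to 13.5 for two. A shift of 2% to 5% is minor beside that, and the study is descriptive.

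4. **The remedy belongs in an analysis plan.** This stands only in part. Delayed entry and table layouts could be settled there, but the protocol itself fixes a start date that contradicts its own definition of follow-up.

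**Conclusion.** The inconsistency is real and is written into the protocol. Observation starts at enrolment and adverse-event collection at consent, while the primary and on-treatment person-time, the adverse-event window and survival all start at the first dose.

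To the extent that pre-enrolment infections are not counted, the rates and their upper bounds are biased low. With lags of 15 days on average (30 days for everyone as the limit) and constant hazard, the primary effect is 2.3% (4.6%) and the zero-event upper bound is about 7.1 (7.2) instead of 6.9 per 1000 patient-years. The on-treatment effect is about 7% (14%), given 6 months of treatment. Adverse events before consent are missed by an amount the protocol does not allow one to estimate. Survival is biased slightly upward.

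These sizes do not support a claim that the primary result is invalid or that the study cannot meet its aim. I rate this as something that should be fixed because the bias runs towards understating risk and the correction is easy. It does not have to be fixed for the study to be interpretable.

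**What to change.** - **Rates (8.3.2.2 and 8.7.2.4).** Start person-time for the primary and both on-treatment rates at the later of enrolment and first dose, and count only events from that date. Report any linked positive swab from before enrolment separately, so that it is not lost.
- **Survival.** Keep the first dose as the time origin, and let each patient enter the Kaplan-Meier risk set at enrolment if that is later.
- **Adverse events.** Tabulate on-treatment incidence separately for patients who consented on or before the first dose and for those who consented after it.
- **End of follow-up.** Leave the 5-year limit anchored to the first dose.
- **Reporting.** Give the distribution of the lag from first dose to enrolment, which replaces the assumption made here.

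**Cost.** One derived start date from dates already collected, with no added visits or samples. Denominators shrink by a few percent: about 12 (25) of 535 patient-years in the scenarios above. The change does not recover what happened before enrolment. If early risk differs from later risk, the first weeks of late enrollers remain unrepresented, and the report should say so.

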8.7.2.4.2 Analysis of the Secondary Endpoints

 Count of herpetic infections with detection of talimogene laherparepvec DNA among close contacts and HCPs

Separate counts will be reported for the number of suspected herpetic infections that are detectable for talimogene laherparepvec DNA in close contacts and HCPs.

 Incidence rate of herpetic infection with detection of talimogene laherparepvec DNA among patients during treatment with IMLYGIC

The incidence rate will be calculated as the number of suspected herpetic infections that are detectable for talimogene laherparepvec DNA divided by sum of follow-up time during treatment period with IMLYGIC dose. If patients receive IMLYGIC over multiple treatment phases, the treatment period is defined as the sum of time from the date of first IMLYGIC dose to 30 days after the date of last IMLYGIC dose or the day before the subsequent treatment phase, whichever comes first, in each treatment phase in patient-years. As a measure of precision, a 95% confidence interval will be calculated around the incidence rate.

 Incidence rate of herpetic infection with detection of talimogene laherparepvec DNA among patients after discontinuation of IMLYGIC

The incidence rate will be calculated as the number of suspected herpetic infections that are detectable for talimogene laherparepvec DNA divided by sum of follow-up time after discontinuation of IMLYGIC (last date of follow-up minus the date of last IMLYGIC dose plus 31 days). If patients receive IMLYGIC over multiple treatment phases, each post-treatment period is defined as sum of time from 31 days after date of last IMLYGIC dose in the prior treatment phase to one day prior to the date of the first IMLYGIC dose in the subsequent treatment phase or the end of study in patient-years. As a measure of precision, a 95% confidence interval will be calculated around the incidence rate.

 Incidence rate of herpetic infection with detection of wild-type HSV-1 among patients during treatment with IMLYGIC

The incidence rate will be calculated as the number of suspected herpetic infections that test positive for wild-type HSV-1 divided by sum of follow-up time during treatment period with IMLYGIC (the date of last IMLYGIC dose plus 30 days minus the date of first

Protocol Number: 20130193 Date: 12 October 2022

Page 29 of 62

IMLYGIC dose). If patients receive IMLYGIC over multiple treatment phases, the treatment period is defined as the sum of time from the date of first IMLYGIC dose to 30 days after the date of last IMLYGIC dose or the day before the subsequent treatment phase, whichever comes first, in each treatment phase in patient-years. As a measure of precision, a 95% confidence interval will be calculated around the incidence rate.

 Incidence rate of herpetic infection with detection of wild-type HSV-1 among patients after discontinuation of IMLYGIC

The incidence rate will be calculated as the number of suspected herpetic infections that test positive for wild-type HSV-1 divided by sum of follow-up time (last date of follow-up minus the date of last IMLYGIC dose plus 31 days). If patients receive IMLYGIC over multiple treatment phases, each post-treatment period is defined as sum of time from 31 days after date of last IMLYGIC dose in the prior treatment phase to one day prior to the date of the first IMLYGIC dose in the subsequent treatment phase or the end of study in patient-years. As a measure of precision, a 95% confidence interval will be calculated around the incidence rate.

Summary of patient characteristics

Demographic and clinical characteristics will be summarized using categorical (n and %) and continuous statistics (n, mean, standard deviation, median, quartiles, minimum and maximum).

• Treatment patterns of anticancer therapy (eg, types and sequence)

The number, types, and order of treatments received will be reported.

Incidence of use of antiherpetic therapy

Patient incidence (n and %) of use of antiherpetic therapy will be reported.

 Incidence of adverse events and serious adverse events during treatment with IMLYGIC

Patient incidence (n and %) of adverse events and serious adverse events occurring between the date of first IMLYGIC dose and the date of last IMLYGIC dose plus 30 days will be reported. If patients receive IMLYGIC over multiple treatment phases, the adverse events and serious adverse events collection period is defined as the date of first IMLYGIC dose to 30 days after the date of last IMLYGIC dose or the day before the subsequent treatment phase, whichever comes first, in each treatment phase

 Incidence of adverse events and of serious adverse events related to IMLYGIC after the treatment period with IMLYGIC

Protocol Number: 20130193 Date: 12 October 2022

Page 30 of 62

Patient incidence (n and %) of adverse events and serious adverse events occurring after the date of last IMLYGIC dose plus 31 days will be reported. If patients receive IMLYGIC over multiple treatment phases, the adverse events and serious adverse events collection period is defined as 31 days after date of last IMLYGIC dose in the prior treatment phase to one day prior to the date of the first IMLYGIC dose in the subsequent treatment phase or the end of study.

Overall survival

Overall survival will be estimated using the Kaplan-Meier method with the time to death being calculated from the date of the first IMLYGIC dose.

Patients who are alive or lost to follow-up at the time of the analysis will be censored.

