The incidence rate will be summarized for positive tests occurring from the date of first IMLYGIC dose to the date of last IMLYGIC dose + 30 days. If patients receive IMLYGIC over multiple treatment phases, the treatment period is defined as the sum of time from the date of first IMLYGIC dose to 30 days after the date of last IMLYGIC dose or the day before the subsequent treatment phase, whichever comes first, in each treatment phase.

 Incidence rate of herpetic infection with detection of wild-type HSV-1 among patients after discontinuation of IMLYGIC

The incidence rate will be summarized for positive tests occurring from 31 days after the last dose of IMLYGIC through the end of follow-up. If patients receive IMLYGIC over multiple treatment phases, each post-treatment period is defined as sum of time from 31 days after date of last IMLYGIC dose in the prior treatment phase to one day prior to the date of the first IMLYGIC dose in the subsequent treatment phase or the end of study.

Summary of patient characteristics

The following baseline variables will be recorded: sex, age, **race**, **ethnicity**, Eastern Cooperative Oncology Group (ECOG) performance status, and disease stage.

Treatment patterns of anticancer therapy (eg, types and sequence)

Page 23 of 62

footnote "f" in Table 1.

Product: IMLYGIC®

Protocol Number: 20130193 Date: 12 October 2022

For more detail on what types of anticancer therapies will be recorded, please refer to

• Incidence of use of antiherpetic therapy

For more detail on what types of antiherpetic therapy will be recorded, please refer to footnote "k" in Table 1.

 Incidence of adverse events and serious adverse events during treatment with IMLYGIC

Adverse events and serious adverse events (as defined in Section 11) that occur from the date of first IMLYGIC dose to the date of last IMLYGIC dose + 30 days. If patients receive IMLYGIC over multiple treatment phases, the adverse events and serious adverse events collection period is defined as the date of first IMLYGIC dose to 30 days after the date of last IMLYGIC dose or the day before the subsequent treatment phase, whichever comes first, in each treatment phase.

 Incidence of adverse events and serious adverse events related to IMLYGIC after discontinuation of IMLYGIC

Adverse events and serious adverse events (as defined in Section 11) that occur more than 31 days after the last dose of IMLYGIC and attributed to IMLYGIC by the physician.

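### Section 8.7.2.4.2 states post-treatment, on-treatment and adverse-event windows that do not match the protocol's own period definitions: missing brackets, a missing end-of-follow-up limit and an unassigned day 31

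*Protocol*

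**What the plan says.** **Post-treatment time.** Section 8.3.2.2 defines the talimogene laherparepvec DNA rate after discontinuation over results "during the period from 31 days after the last dose of IMLYGIC through the end of follow-up", and the wild-type HSV-1 rate is defined the same way. Section 8.7.2.4.2 then gives the denominator as "last date of follow-up minus the date of last IMLYGIC dose plus 31 days". The wild-type bullet repeats it: "divided by sum of follow-up time (last date of follow-up minus the date of last IMLYGIC dose plus 31 days". In both bullets the next sentence, for patients with several treatment phases, says "each post-treatment period is defined as sum of time from 31 days after date of last IMLYGIC dose in the prior treatment phase". That sentence ends the time at the day before the next phase or at the end of study.

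**On-treatment time.** Section 8.3.2.2 runs it "from the date of first IMLYGIC dose to the date of last IMLYGIC dose + 30 days". For wild-type HSV-1, Section 8.7.2.4.2 spells out the calculation as "the date of last IMLYGIC dose plus 30 days minus the date of first" dose. The multi-phase rule adds one further limit, the day before the next phase. Section 8.2.5 ends a patient's follow-up at the earliest of 5 years after first dose, death, withdrawal of consent or loss to follow-up.

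**Adverse events.** The on-treatment window closes 30 days after the last dose. Post-treatment related events are those that "occur more than 31 days after the last dose of IMLYGIC and attributed to IMLYGIC by the physician" (Section 8.3.2.2), and Section 8.7.2.4.2 likewise counts events after the last-dose date plus 31 days. The multi-phase rule in both sections starts at 31 days. Table 1 footnote n collects related "Adverse events and serious adverse events that occur more than 30 days after the last dose of IMLYGIC".

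**The concern.** These are explicit calculation rules, so a programmer may follow them as printed. Taken literally, the post-treatment formula lengthens the denominator and lowers both post-treatment infection rates. An on-treatment formula that does not stop at death or loss errs in the same direction. In a safety study required by regulators, understating a rate is the less acceptable error. The day-31 gap is of a different kind: an event that the protocol collects has no analysis period to be counted in.

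**Working it through.** **The plan's own figures first (Section 8.5).** At 3 per 1000 patient-years (PY) and 535 PY, the probability of at least one event is 1 − exp(−0.003 × 535) = 79.9%, stated as 80%. The zero-event upper bound is 3.689 / 535 = 6.90 per 1000 PY, stated as 6.9. Both reproduce. Neither uses the windows discussed here.

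**One patient.** Let FD = first dose = day 0, LD = last dose = day 182, LFU = last follow-up = day 730 (illustrative values).

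- On-treatment: LD + 30 − FD = 212 days.
- Post-treatment, left to right: 730 − 182 + 31 = 579 days. Sum with on-treatment: 791 of 730 available days.
- Post-treatment, grouped: 730 − (182 + 31) = 517 days. Sum: 729.
- Difference: 579 − 517 = 62 days.
- Grouped, counting day 31 itself (+1): 518 days. Sum: 730, which equals the primary denominator in Section 8.7.2.4.1 (last follow-up minus first dose).

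**A patient who leaves early.** Same FD and LD, LFU = day 192.

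- On-treatment as printed: 212 days. Limited at LFU: 192 days.
- Post-treatment, grouped: 192 − 213 = −21 days, or −20 with the +1. Adding brackets alone is therefore not enough; a floor at 0 is needed.

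**Cohort size of the bracket problem, if programmed literally.** Inputs from the protocol: about 300 patients and 535 PY (Section 8.5), and a median treatment of about 6 months in the trial setting (design schema footnote). Assumptions: that median used as a mean, varied from 0.25 to 0.75 year, and 70% to 100% of patients contributing post-treatment time. Total PY is held at 535.

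- Maximum excess: 62 × 300 / 365.25 = 50.9 PY.
- On-treatment at 0.5 year: 300 × (0.5 + 30/365.25) = 174.6 PY.
- Post-treatment, grouped: 535 − 174.6 − 300/365.25 = 359.5 PY.
- Literal, all patients contributing: 359.5 + 50.9 = 410.5 PY (unrounded inputs). Rate ratio 359.5 / 410.5 = 0.876, so about 12% too low.
- Zero-event upper bound: 3.689 / 359.5 = 10.26 per 1000 PY, against 3.689 / 410.5 = 8.99.

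| Mean treatment (years) | Share contributing | Post-treatment PY, grouped | Post-treatment PY, literal | Rate ratio |
|---|---|---|---|---|
| 0.25 | 70% | 434.5 | 470.2 | 0.924 |
| 0.50 | 100% | 359.5 | 410.5 | 0.876 |
| 0.75 | 100% | 284.5 | 335.5 | 0.848 |

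Across the range the understatement is about 8% to 15%.

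**On-treatment over-run.** Assume 5% to 30% of patients end follow-up within 30 days of the last dose, on average 15 days early.

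- 5%: 300 × 0.05 × 15 / 365.25 = 0.62 PY, or 0.4% of 174.6.
- 30%: 300 × 0.30 × 15 / 365.25 = 3.7 PY, or 2.1%.

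**Adverse events, single-phase patient.** Day 30 is on-treatment. Day 31 is collected under footnote n but is neither within 30 days nor more than 31 days after the last dose. Day 32 is post-treatment. Under the multi-phase rule, day 31 is post-treatment. The gap is exactly one day.

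**The case against.** The strongest reply is that nobody reading the whole section would program the additive version. Section 8.3.2.2 fixes the start at 31 days after the last dose, the sentence after each formula says the same for multi-phase patients, and the adverse-event text treats the last-dose date plus 31 days as a single date. The additive version also gives more days than the patient was followed, which a routine check would show. This stands as to intent. It does not remove the conflict: the printed expression still needs brackets, and the sentence after it is conditional on several treatment phases.

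On the second item, a reader might infer that on-treatment time always runs past death or loss. The documents do not support that. Both on-treatment denominators are described as follow-up time, which Section 8.2.5 ends at death, withdrawal or loss, and the talimogene laherparepvec DNA bullet prints no subtraction formula. What stands is narrower: the wild-type bullet spells out a calculation without that limit. Similarly, the end of study in the multi-phase rule could mean the patient's own end, as the Appendix B form uses the term. But Section 8.2.1 ties the end of the study period to the last enrolled patient, so the term is ambiguous.

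On the third item, it is fair to say that no data are lost, that only single-phase patients are touched, and that one day matters little.

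**Conclusion.** The windows in Section 8.7.2.4.2 are wrong as written against the protocol's own definitions, in three places of unequal weight.

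- The unbracketed post-treatment formula is the main one. It affects both post-treatment infection rates, by roughly 8% to 15% downward, only if programmed literally and under the assumed treatment duration and share contributing.
- The missing end-of-follow-up limit in the wild-type on-treatment formula is worth about 0.4% to 2% under the assumed share of early leavers. The multi-phase end point should also name the patient's end of follow-up.
- The day-31 gap is a one-day inconsistency for related adverse events in single-phase patients.

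A reader might infer that every rate in the study is biased low. That does not follow: the primary endpoint is last follow-up minus first dose, and it and the 535 PY, 80% and 6.9 per 1000 do not depend on these windows. Nor do the documents show a planned bias, since the definitions reveal the intended grouping. Severity is low.

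**What to change.** - **Post-treatment time:** max(0, end date − (date of last dose in the phase + 31 days) + 1). The end date is the earlier of the day before the next phase and the patient's own end of follow-up under Section 8.2.5. Use that term in place of the end of study.
- **On-treatment time:** from the first dose of the phase to the earliest of last dose + 30 days, the day before the next phase, and the patient's end of follow-up. State this once and apply it to both infection endpoints.
- **Time origin:** keep first dose, as in Sections 8.3.2.2 and 8.7.2.4.1. Use one day-counting convention in every phase, so that each patient's on- and post-treatment days sum to the primary denominator. That sum is also a simple programming check.
- **Post-treatment related adverse events:** on or after day 31, in Sections 8.3.2.2 and 8.7.2.4.2, in line with footnote n and the multi-phase rule.

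The cost is wording and programming only. Data collection, sample size and the primary analysis do not change.
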